10 ETHICS/PROTECTION OF HUMAN SUBJECTS

10.1 INSTITUTIONAL REVIEW BOARD

This protocol, the written informed consent form, and any materials presented to subjects shall be submitted to the IRB identified with this responsibility. Notification in writing of approval must come from the IRB chairman or secretary, to the investigator, either as a letter or as a copy of the appropriate section of the IRB meeting minutes where this protocol and associated informed consent form were discussed. The investigator will not participate in the decision. If the investigator is an IRB member, the written approval must indicate such non-participation in the voting session. The investigator will submit status reports to the IRB as required by the governing body. The IRB must be notified by the investigator in writing of the interruption and/or completion of the study; the investigator must promptly report to the IRB all changes in research (protocol amendments) and will not make such changes without IRB approval, except where necessary to eliminate apparent immediate hazards to human subjects. In cases where it is necessary to eliminate immediate hazards to subjects, the IRB must then be notified of the change as per local requirements. The investigator is required to maintain an accurate and complete records of all written correspondence to and received from the IRB and must agree to share all such documents and reports with the Sponsor.

10.2 INFORMED CONSENT PROCESS

10.2.1 CONSENT PROCEDURES AND DOCUMENTATION

Written informed consent will be obtained from all subjects (or their guardian or legally authorized representative) before any study-related procedures (including any pre-treatment procedures) are performed. The investigator(s)

has both ethical and legal responsibility to ensure that each subject (or their guardian or legally authorized representative) being considered for inclusion in this study is given a full explanation of the protocol. This shall be documented on a written informed consent form, which shall be approved by the same IRB responsible for approval of this protocol. Each informed consent form shall include the elements required by CRF21 part 50.25 and any applicable local regulations. The investigator agrees to obtain approval from the Sponsor of any written informed consent form used in the study, prior to submission to the IRB.

Once the appropriate essential information has been provided to the subject and fully explained by the investigators (or a qualified designee) and it is felt that the subject understands the implications of participating, the subject and the investigator (or designee) shall sign the IRB approved written informed consent form. The subject shall be given a copy of the signed informed consent form, and the original shall be filed appropriately, according to the institution. A second copy may be filed in the subject's medical record, if allowed by the institution.

10.3 PARTICIPANT AND DATA CONFIDENTIALITY

All information generated in this study must be considered highly confidential and must not be disclosed to any persons not directly concerned with the study without written prior permission from the Sponsor. However, authorized regulatory officials and Sponsor personnel will be allowed full access to the records.

Only unique subject numbers in eCRFs will identify subjects. Their full names may, however, be made known to a product regulatory agency or other authorized official if necessary.

11 DATA HANDLING AND RECORD KEEPING

11.1 DATA COLLECTION AND MANAGEMENT RESPONSIBILITIES

Data collection will be with an electronic CRFs (eCRF). All users will be trained on the technical features of the EDC (Electronic Data Capture) as well as the content of the eCRF by qualified personnel prior to gaining access to the EDC. An User ID/Password will be granted after training. This ID is not to be shared amongst the study staff. The CRFs may be completed by clinical site personnel who have been authorized by the principal investigator and whose names are documented on the Signature Log,

Prior to the database being locked, the investigator or designee will review, approve, and sign/date each completed eCRF. This signature serves as attestation of the Investigator's responsibility for ensuring that all data entered into the eCRF are complete, accurate, and authentic. After the end of the trial, a copy of the CRF data will be provided to the site. This copy will contain the final data, an audit trail of activity on the data, and any queries and answers that were posted for data clarification.

11.2 STUDY RECORDS RETENTION

All clinical sites will maintain study records for a minimum of two years after termination of the study. The investigator shall take responsibility for maintaining adequate and accurate hard copy source documents of all observations and data generated during this study, including any data clarification forms (DCFs) received from the Sponsor. Such documentation is subject to inspection by the Sponsor or its agents, and/or other regulatory agencies.

11.3 PROTOCOL DEVIATIONS

This study will be conducted as described in this protocol, except for an emergency situation in which the protection, safety, and well-being of the subject requires immediate intervention, based on the judgment of the investigator (or a responsible, appropriately trained professional designated by the investigator). In the event of a significant deviation from the protocol due to an emergency, accident, or mistake, the investigator or designee must contact the C5Research team within 5 days of the incident. This will allow an early joint decision regarding the subject's continuation in the study. The investigator and the Sponsor will document this decision. The IRB will be informed of all protocol changes by the investigator in accordance with the IRB established procedure.

11.4 PUBLICATION AND DATA SHARING POLICY

Publications addressing the WATCH-TAVR study will be managed by the study Steering Committee. The scientific validity and timing of publications will be evaluated in order to maximize the benefits derived from the publication of the worldwide clinical data of the study.

At the conclusion of the study, a multicenter abstract reporting the primary results will be prepared and presented at a major cardiovascular meeting. A multicenter publication will also be prepared for publication in a reputable scientific journal. We anticipate many secondary manuscripts with principal authorship drawn from members of the Steering Committee and Investigative sites. For purposes of timely abstract presentation and publication, such secondary publications will be delegated to the appropriate principal authors, and final analyses and manuscript review for all multicenter data will require the approval of the Steering Committee.

12 STUDY ADMINISTRATION

A Steering Committee consisting of academic experts who participated in the development of the protocol and/or will provide ongoing scientific and operational oversight to the study. This Committee will monitor progress of study enrollment, make recommendations to the Sponsors based on the Medical Monitor recommendations, and oversee the presentation and publication of the trial results. The membership, roles and responsibilities will be described in the SC Charter.

1 INTRODUCTION

1.1 Preface

Atrial fibrillation (AF) is a common baseline comorbidity and the commonest arrhythmia in patients with aortic stenosis (AS) undergoing Transcatheter Aortic Valve Replacement (TAVR). The TAVR population is at increased long-term bleeding risk, with cognitive impairment, high risk of falls, history of spontaneous bleeding, etc. Standard medical therapy for emboli prevention in AF, long term oral anticoagulation (OAC), carries risk of hemorrhagic stroke, as well as major bleeding complications [1]. The WATCHMAN Left Atrial Appendage Closure (LAAC) System is the only device that has been approved by the FDA for preventing thrombo-embolic events in patients with non-valvular atrial fibrillation (AF) [2]. The WATCHMAN device has shown improved safety compared to OAC, with reduced event rates for hemorrhagic stroke and major bleeding in patients receiving the implant [3, 4]. However given the previous WATCHMAN device trials excluding patients with valvular heart disease, data on safety and efficacy of the device in TAVR patients with AF is lacking [5].

1.2 Scope of the analyses

These analyses will investigate the safety and effectiveness of the left atrial appendage occlusion with WATCHMAN Device in prevention of stroke and bleeding in AF patients undergoing TAVR. We will evaluate this by the primary composite endpoint (all-cause mortality, stroke and life-threatening/major bleeding events) for both TAVR and WATCHMAN.

2 STUDY OBJECTIVES AND ENDPOINTS

2.1 Study Objectives

We aim to demonstrate the non-inferiority of TAVR plus WATCHMAN group in terms of the primary composite endpoint, compared to TAVR alone group.

2.2 Endpoints

2.2.1 Primary endpoint

The primary endpoint is the first occurrence of all-cause mortality, stroke or major/life-threatening bleeding event following randomization.

[figure not shown]
2.2.2 Secondary endpoints

1. Time from randomization to each component of the primary endpoint: all-cause mortality, any stroke and any occurrence of major or life-threatening bleeding (as per VARC2 definition of bleeding).
2. Time to death from cardiovascular causes
3. Time to ischemic stroke
4. Time to hemorrhagic stroke
5. Arterial or venous thrombosis or embolism
6. Rehospitalization related to WATCHMAN procedure or WATCHMAN device.

3 STUDY METHODS

3.1 General Study Design and Plan

WATCH-TAVR is a prospective, multicenter, randomized event-driven controlled trial. Only centers with approval for commercial WATCHMAN implantation will be included in this trial. Subjects will be enrolled at approximately 33 centers in the United States. There will be approximately 350 subjects enrolled, with 175 patients being randomized to TAVR + medical therapy and 175 patients randomized to simultaneous TAVR+WATCHMAN to accumulate the 191 primary events needed. Patients with non-valvular AF undergoing standard of care TAVR will be enrolled in the trial. Patients randomized to receive the WATCHMAN device will receive anticoagulation with warfarin and aspirin for 6 weeks after the procedure. After 6 weeks, the plan of care will follow WATCHMAN labeling. Patients randomized to the TAVR + medical therapy arm will be treated in accordance with standard of care with either warfarin, other anticoagulant/antiplatelet therapy, or no anticoagulation at the discretion of the treating physician. All patients will continue to receive routine post-TAVR follow-up and care. Patients will be monitored for primary and secondary endpoints as outlined. Baseline information and laboratory data will be collected as described in the protocol.

3.2 Inclusion-Exclusion Criteria and General Study Population

3.2.1 Inclusion Criteria

Patients who fulfill the following criteria will be included: Determination for participation in the study is based upon standard of care practice for assessment of TAVR & WATCHMAN eligibility [6].

1. Men and Women \geq 18 years of age
2. The patient meets criteria for and is eligible to undergo TAVR procedure
3. The patient has documented paroxysmal, persistent, or permanent atrial fibrillation
4. The patient meets the WATCHMAN labeling guidelines and is eligible to undergo the WATCHMAN implantation procedure
5. The patient is eligible for short term warfarin therapy
6. The patient or legal representative is able to understand and willing to provide written informed consent to participate in the trial
7. The patient is able and willing to return for required follow-up visits and examinations

3.2.2 Exclusion Criteria

Any patient who fulfills any of these criteria shall be excluded [6]:

1. The patient had a stroke or TIA within the last 6 months prior to enrollment
2. Contraindication for short term anticoagulation
3. Moderate or severe MS with mean gradient across MV >10 mm Hg or MVA $< 1.2\text{cm}^2$.
4. The patient has symptomatic carotid disease (i.e., carotid stenosis $\geq 50\%$ associated with ipsilateral transient or visual TIA evidenced by amaurosis fugax, ipsilateral hemispheric TIAs or ipsilateral stroke within 6 months)
5. Prior occlusion of LAA
6. The patient has an implanted mechanical mitral valve
7. The patient requires long-term warfarin therapy due to:
 - a. Secondary to conditions such as prior arterial embolism or other indications such as pulmonary embolism or deep vein thrombosis within the previous 6 months.
 - b. The patient is in a hypercoagulable state; exclude the patient if per medical record documentation, the patient meets any of the following criteria:
 - Thrombosis occurring at a young age (i.e. less than 40 y/o)
 - Idiopathic or recurrent VTE (venous thrombo-embolism)
 - Thrombosis at an unusual site (cerebral veins, hepatic veins, renal veins, IVC, mesenteric veins)
 - Family history of VTE or of inherited prothrombotic disorder, recurrence/extension of thrombosis while adequately anticoagulated.
8. The patient is actively enrolled in another trial of a cardiovascular device or an investigational drug (post-market study participation and registries are acceptable)
9. The patient is pregnant or pregnancy is planned during the course of the investigation if patient is of child bearing potential.
10. Any clinically significant medical condition or presence of any laboratory abnormality prior to randomization that is considered by the investigator to be clinically important and could interfere with the conduct of the study or not meeting procedure guidelines for TAVR or Watchman.
11. The patient has a life expectancy of less than two years.

3.2.3 General Study Population

350 patients having non-valvular AF undergoing standard care of TAVR

3.3 Study Assessments

All study assessments for both TAVR plus WATCHMAN combined arm and TAVR only arm are summarized in these two tables shown below.

Study Assessment	Visit after TAVR plus WATCHMAN procedure				
	Visit 1	Visit 2	Visit 3	Visit 4	Visit 5 ¹
	Baseline	45 days (± 15 days)	6 Months (± 1 month)	12 Months (± 1 month)	24 Months (± 1 month)
Informed Consent	+				
Inclusion/Exclusion Criteria	+				
Randomization	+				
WATCHMAN Procedure	+				
TEE ²	+ (during WATCHMAN procedure)	+			
KCCQ-12 Score	+	+	+	+	+
Vital Signs	+	+	+	+	+
AE Monitoring	+	+	+	+	+
INR	+	+	+ ³	+ ³	+ ³
Blood Work	+ ⁴				
NIH Stroke Scale (NIHSS)	+	+	+	+	+
Modified Rankin Scale (MRS)	+	+	+	+	+
Brain Image (CT or MRI) ⁵	As Required				
Neuro Assessment ⁶	As Required				

1. May be visit or phone follow up.
2. TEE during the WATCHMAN procedure and 45 days (+/-15 days) after the WATCHMAN Procedure. Patients randomized to WATCHMAN who have intracardiac thrombus visualized are contraindicated from receiving the device per labeling guidelines, but will remain in the trial as intent to treat and should be followed for all study visits.
3. If patient continues to be on warfarin.
4. Tests include serum creatinine, platelet count and hemoglobin level. To be obtained within 7 days of randomization/WATCHMAN Procedure.
5. Required following a Stroke or TIA event including neurological assessment by a Neurologist.
6. Neurological assessment by neurologist if a patient experiences a stroke or TIA throughout the duration of the study.

Study Assessment	Visit after TAVR ALONE procedure				
	Visit 1	Visit 2	Visit 3	Visit 4	Visit 5 ¹
	Baseline	45 days (± 15 days)	6 Months (± 1 month)	12 Months (± 1 month)	24 Months (± 1 month)
Informed Consent	+				
Inclusion/Exclusion Criteria	+				
Randomization	+				
KCCQ-12 Score	+	+	+	+	+
Vital Signs	+	+	+	+	+
AE Monitoring	+	+	+	+	+
INR	+	+	+	+	+ ²
Blood Work	+ ³				
NIH Stroke Scale (NIHSS)	+	+	+	+	+
Modified Rankin Scale (MRS)	+	+	+	+	+
Brain Image (CT or MRI) ⁴	As Required				
Neuro Assessment ⁵	As Required				

1. May be visit or phone follow up
2. If patient continues to be on warfarin
3. Tests include serum creatinine, platelet count and hemoglobin level. To be obtained within 7 days of randomization.
4. Required following a Stroke or TIA event including neurological assessment by a Neurologist.
5. Neurological assessment by neurologist if a patient experiences a stroke or TIA throughout the duration of the study.

4 SAMPLE SIZE

This randomized control trial will aim to prospectively enroll 350 patients having non-valvular AF undergoing standard care of TAVR. The control group consists of patients undergoing TAVR who are on standard medical practice, with oral anticoagulation at the discretion of the treating physician. The treatment group will have the WATCHMAN implantation procedure performed simultaneously with TAVR. The primary endpoint is a composite of all-cause mortality, stroke, life-threatening or major bleeding. The objective of the study is to demonstrate non-inferiority of the TAVR plus WATCHMAN device compared to the TAVR only group.

The following assumptions were used to determine the sample size needed to assess the non-inferiority hypothesis for the composite primary endpoint of all-cause mortality, stroke or major or life-threatening bleeding:

- One-sided $\alpha = 0.025$
- Primary event rate in the control population (TAVR only) of 35% at one year
- Non-inferiority margin of 1.5
- Underlying hazard ratio of active to control is 1.0
- Power at least 80%
- Lost to follow-up rate 10%

Assuming level of significance (α) to be 0.05 (or $\alpha = 0.025$ one-sided) and aiming for a study power ($1 - \beta$) of 80%, we estimate 191 primary events will be needed to rule out an upper limit of the one-sided 97.5%

confidence interval of 1.5. Assuming an enrollment duration of 18 months, follow-up period of 24 months, and 10% drop out rate per annum, the minimum total sample size required is 350 (175 per group).

5 GENERAL ANALYSIS CONSIDERATIONS

5.1 Timing of Analyses

The final analysis will be performed when 191 primary events are observed for the primary analysis, or if the study is stopped for administrative reasons.

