9.4.2 ANALYSIS OF THE PRIMARY ENDPOINT

The primary endpoint is the first occurrence of all-cause mortality, stroke or major/life-threatening bleeding event within one year following randomization. Estimates of the hazard ratio and 95% confidence intervals will be based on the Cox proportional hazards model, under the assumption of proportional hazards. Comparison of cumulative hazard functions will be based on the log-rank test.

The upper bound of the confidence interval will be generated from the Cox proportional hazards model with treatment group as a factor.

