5.2 Analysis Populations

Intention-to-Treat Population (ITT):

The primary analysis will be based on the ITT population. All randomized subjects will be analyzed according to their original randomization assignment (WATCHMAN+TAVR or TAVR) regardless of treatment received. The ITT analysis will be censored at 2 years (730 days) after randomization.

Per-protocol population (PP):

The per-protocol population is defined as patients in the WATCHMAN groups who received both the WATCHMAN and the prosthetic valve. In the TAVR only group, it is defined as patients who had the prosthetic valve placed. The PP analysis will be censored at 2 years (730 days) after randomization.

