5.4.2 Durations

- Time to Event (e.g. time to primary endpoint) will be calculated as (event date/time – randomization date/time). Patients not having an event, or lost to follow-up will be censored at the minimum of the time of their last documented follow-up date, death date, or 2 years (730 days).
- Other durations of time will be calculated similarly as (date/time of interest – reference date/time +1)

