5.5 Interim Analyses

No interim statistical analysis will be performed.

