7 ANALYSES

7.1 Primary Analysis

The ITT analysis will include all positively adjudicated post-randomization primary endpoints within the ITT analysis set through 24 months (730 days) after randomization.

The study is designed to demonstrate the non-inferiority of the WATCHMAN device compared to the control group, with regards to the primary endpoint (composite of all-cause mortality, stroke (ischemic and hemorrhagic), or bleeding (major and/or life-threatening)). Non-inferiority will be assessed using the 1-sided 97.5% confidence interval around the hazard ratio (WATCHMAN-TAVR: TAVR only). Non-inferiority will be demonstrated if the 1-sided 97.5% upper confidence limit for the difference in proportions is less than 1.5. If the non-inferiority objective is met, additional analyses to assess superiority of the WATCHMAN group to the control group will be performed. The composite primary endpoint will also be summarized as events per 100 patient-years of follow-up.

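### The final analysis waits for 191 primary events or an undefined administrative stop, but the SAP counts nothing after day 730 in about 350 patients, so the event trigger can become impossible to meet

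*SAP*

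**What the plan says.** The protocol summary and SAP 3.1 describe an event-driven trial of about 350 patients enrolled to accumulate 191 primary events. SAP 5.1 gives the timing rule: "The final analysis will be performed when 191 primary events are observed for the primary analysis, or if the study is stopped for administrative reasons". SAP 5.5 adds "No interim statistical analysis will be performed", so this is the only planned analysis.

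The counting window is closed in three places:

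- SAP 5.2: "The ITT analysis will be censored at 2 years (730 days) after randomization".
- SAP 5.4.2 censors event-free patients at "the minimum of the time of their last documented follow-up date, death date, or 2 years (730 days").
- SAP 7.1 includes adjudicated endpoints "within the ITT analysis set through 24 months (730 days) after randomization".

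Protocol 9.4.2, by contrast, defines the primary endpoint as a first event "within one year following randomization".

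On drop-out, SAP 4 and protocol 9.4.4 each give two statements. The assumption list has "Lost to follow-up rate 10" per cent, with no time unit. The sentence that produces the sample size has "10% drop out rate per annum, the minimum total sample size required is 350 (175 per group"). Neither document says when during the year losses are taken to occur.

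**The concern.** An event-driven rule works if follow-up can run on until the target is reached. Here it cannot: each patient contributes at most 730 days, and no text provides for enlarging enrolment or extending the window. The count therefore has a ceiling, fixed when the last patient passes day 730 or leaves. If that ceiling is below 191, the first limb of SAP 5.1 can never be satisfied. The second limb has no criterion. Protocol 9.4.1 has patients followed until study termination but does not say when that is.

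At stake is a pre-specified time for the single analysis of an open comparison. Under the one-year wording in protocol 9.4.2 the conflict is sharper, because the target then lies far outside what 350 patients can produce.

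**Working it through.** **Inputs** (SAP 4 and protocol 9.4.4): one-sided alpha 0.025, power 80%, margin 1.5, true hazard ratio 1.0, control risk 35% at one year, 350 patients. Allocation is 1:1 (protocol 6.1.1). Counting stops at day 730 (SAP 5.2, 5.4.2, 7.1). *Assumptions:* constant hazard into the second year, since the plan gives no second-year rate; drop-out independent of events; no events counted after drop-out.

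**Step 1: the plan's 191.** Events = 4 × (1.960 + 0.8416)² / (ln 1.5)² = 190.97, rounded up to 191. Reproduced.

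**Step 2: expected events by day 730.** The event hazard is h = −ln(0.65) = 0.4308 per year. With a continuous loss hazard d, the fraction with a counted event by T years is h/(h+d) × [1 − exp(−T(h+d))]. Power at D events is Φ(√D × ln 1.5 / 2 − 1.960). The chance of fewer than 191 is the binomial probability of at most 190 among 350.

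| Reading of the 10% loss (T = 2) | Fraction | Events from 350 | Power | Chance of fewer than 191 | N to expect 191 |
|---|---|---|---|---|---|
| Per annum, continuous (d = −ln 0.9 = 0.1054) | 0.5285 | 185.0 | 78.7% | 72% | 362 |
| Over two years, continuous (d = 0.0527) | 0.5522 | 193.3 | 80.5% | 38% | 346 |
| Per annum, removed at month 12 | 0.5548 | 194.2 | 80.6% | 35% | 345 |
| No loss (for reference) | 0.5775 | 202.1 | 82.2% | 10% | 331 |

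The third row is 0.35 + 0.65 × 0.90 × 0.35 = 0.5548. As a check on the first row, √185 × 0.4055 / 2 = 2.757, and Φ(2.757 − 1.960) = 0.787.

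Two readings support a minimum of 350. Continuous 10% per annum needs about 3% more (362/350 = 1.034).

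**Step 3: sensitivity to the event rate.** At an assumed one-year risk of 30%, the expected count is 163 (continuous 10% per annum) to 179 (no loss), and the chance of reaching 191 is 0.2% to 10%.

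**Step 4: the one-year window in protocol 9.4.2.** With T = 1, the count is 116.7 (continuous 10% per annum) to 350 × 0.35 = 122.5 (no loss). Power is 59.1% to 61.2%. Expecting 191 would need 546 to 573 patients; with 350 the chance of reaching it is negligible.

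**The case against.** The strongest reply is that the gap has little practical effect. Participant duration is two years, and SAP 7.1 takes in all adjudicated endpoints through day 730, so the natural end is the last patient's 24-month follow-up. Once everyone has passed day 730, a later analysis date hardly changes the data. With no interim analysis, no alpha problem is shown. Any trial can be stopped for administrative reasons. Most of this stands, and it limits the size of the point. It does not supply the missing rule: SAP 5.1 does not name the last patient's day 730 as a trigger.

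A reader might infer from the 185 that the sample size is an arithmetic error. The documents do not support that. They call 350 approximate and a minimum, and it reproduces with the 10% spread over two years, or taken per annum with losses removed at month 12. Nor is the two-year reading the only one that works, as the month-12 row shows.

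A reader might also infer that an early administrative stop is likely. Nothing in the documents suggests one. Likewise, the vital-status check in protocol 4.4 could add deaths after drop-out, but SAP 5.4.2 does not say whether they count, and the mortality figures in protocol 9.4.4 carry no time unit. I put no number on that.

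Finally, analysing at event 191 can leave some patients short of day 730. True, but SAP 5.1 already has that feature; the added trigger does not create it.

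**Conclusion.** The point holds as an incomplete analysis-timing rule and a contradictory endpoint window. It does not show a seriously underpowered trial. The event trigger and the 730-day cap can conflict. At the planning rates the chance of falling short of 191 is 35% to 38% or 72%, depending on how the stated 10% loss is read. At full two-year follow-up the power cost is at most about 1 point (78.7% against 80%). These figures rest on a constant hazard, a hazard ratio of 1.0 and no events counted after drop-out. A lower event rate would make a shortfall more likely.

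The one-year wording in protocol 9.4.2 is a separate contradiction with the SAP. Taken literally, it puts 191 out of reach and power near 60%. The 24-month follow-up in protocol 9.4.4 and the SAP's 730 days indicate that two years is the working definition, so those one-year figures show why the texts must agree. They are not a forecast for the trial.

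**What to change.** 1. Align protocol 9.4.2 with the SAP's 730-day window. Do this first, because every restated figure depends on it.
2. In SAP 5.1, state that the final analysis is performed when 191 positively adjudicated primary events have occurred, or when the last randomized patient has reached day 730 or exited, whichever comes first. Tying the trigger to adjudicated events matches what SAP 7.1 counts. Define the administrative reasons or delete that limb.
3. In protocol 9.4.4 and SAP 4, give one drop-out basis with its time unit and the convention for when losses occur. State the matching expected events and power for 350 patients under the 730-day cap: about 185 events and 79% if loss is a continuous 10% per annum, or about 193 to 194 events and just over 80% on the other two readings.

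This is wording only, with no added patients, visits or follow-up. The downside is that the stated power may have to become about 79%.
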